9. DATA PROCESSING AND ANALYSIS

9.1 Data processing

The CommCare platform will be used for this study. All forms will be programmed by [name] (Monitoring & Evaluation Nutrition Associate and local PI) and the CommCare coding will be verified by an experienced Monitoring & Evaluation Project Specialist. Most data will be collected electronically using tablets and once collected will automatically be transferred and stored on 1AF's account on the CommCare server. All forms will be pretested in the field. Data captured on paper forms first (anthropometry and blood results) will be entered into the tablets in the evening of the same day and together with that day's participant's form uploaded to CommCare. Incoming data will be checked regularly, on a daily base initially, and edited according to query forms.

9.2 Data analysis

The intervention group will be compared to the control group in both studies using the intention to treat approach as this is not a strictly controlled clinical trial and adherence is one of the outcomes.

Data analysis will be done researcher-blinded, meaning that the data analyst will not be provided with the keys to the group assignments before completion of data analysis. A data analysis plan will be elaborated once the study protocol is approved by the ethics committee and well in advance of the actual data analysis.

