We anticipate recruiting 1,200 (600 in each group) pregnant women into the study (see section 11.2 for sample size calculation); this is expected to yield a sufficiently large sample of children later in the study. Women will be recruited from 120 clusters (randomly assigned to intervention or control) that will be drawn from from Kimilili and Webuye districts in Bungoma County in Western Province of Kenya.

The communities will be informed about the study in village meetings by CHVs and by conducting outreach within their catchment area to identify pregnant women. Pregnant women will then be screened by 1AF enumerators. During **screening**, a few questions on health status and pregnancy will be asked. If the woman is prior or equal to 20 weeks of gestation (according to last menstrual period), has no visible severe disease and no allergy to peanuts or milk products, and confirms anticipated residence in the area for the coming 30 months, written informed consent for her and her offspring will be sought from her. She will then be asked to provide a urine sample to confirm pregnancy and she will be enrolled if pregnancy is confirmed. Following the screening, 5 assessment rounds (baseline and 4 follow-up assessments during the intervention) will be conducted at the participant's homes (rounds 1-3) or at a central place (rounds 4 and 5) within walking distance from their homes (Figure 2). Assessment round 3 (immediately) after delivery will be conducted as home visits or clinic visits in case of delivery at a clinic. Details of assessment procedures for each round are illustrated in (Figure 3).

Round 1 (Enrolment, ≤ 20 wk of gestation):

On the day of enrolment the round 1 assessment will be done. As part of this, the following information will be collected: household demographics and characteristics, maternal education; knowledge, attitude and practices (KAP) of specific dietary and nutrition practices during pregnancy; individual dietary diversity; antenatal care; WASH practices; height, weight and mid-upper arm circumference; maternal haemoglobin concentration and malaria parasitaemia from a capillary blood sample. After round 1, participants randomly allocated to the intervention group will start receiving the intervention package.

Round 2 (Gestational age of 34 ± 1 wk):

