In round 2, interview questions related to diet and nutrition KAP during pregnancy, dietary diversity, antenatal care, and WASH will be asked. Additionally, MUAC (mid-upper arm circumference) will be measured and a capillary blood sample for measurement of haemoglobin concentration, malaria parasitaemia and micronutrient status will be provided.

Round 3 (Within 24-48 hours after delivery):

The mother-child pair will be visited within 24-48 hours after delivery. The following information will be recorded: delivery date and time, delivery method, recent antenatal care, and early initiation of breastfeeding. The mother will be assessed for MUAC but no blood sampling will be conducted. For the newborn, head circumference, birth weight and birth length, and haemoglobin concentration (from a heelprick) will be measured.

Round 4 (At 6.5 mo ± 1 mo of age of offspring):

This assessment will be conducted when the child turns 6.5 months old. Breastfeeding and other infant and young child feeding indicators, child morbidity, maternal dietary diversity, postnatal care, and WASH information will be gathered. In mothers, MUAC and weight will be measured and haemoglobin concentration and malaria parasitaemia from a capillary sample will be assessed. In

children, length, weight and head circumference will be measured and a capillary blood sample for haemoglobin concentration, malaria parasitaemia and micronutrient status will be provided.

Round 5 (At 24 ± 1mo of age of offspring):

This assessment will be conducted when the child turns 24 months old. Questionnaire-based information on child feeding, child dietary diversity, child morbidity and WASH will be collected. As in round 4, child length, weight and head circumference will be measured and a fingerprick blood sample will be provided for the measurement of haemoglobin concentration, malaria parasitaemia, and micronutrient status. No maternal biomarkers will be collected at this point.

As part of the monthly visits to the participants' households, the CHV will also collect data on intervention adherence and recent morbidity.

[figure not shown]

Figure 2: Timing of assessment rounds for study 1.

[figure not shown]

Figure 3: Detailed procedures for each assessment round in study 1

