8.2.1 Data collection instruments

In all assessment rounds in study 1 and 2, questionnaires will be administered to the participant or the participants' mother/caregiver by previously trained study staff. The type of modules and in which study they are used are summarized in Table 10.

Table 10: Summary of modules used to collect information through questionnaires.

Module	Study 1	Study 2
Household demographics	X	X
Household characteristics	X	X
Maternal education/occupation	X	X
Maternal information on pregnancies and child birth	X	X
Knowledge, attitude and practices (KAP) of dietary and nutrition practices during pregnancy and lactation	X	
Woman dietary diversity	X	
Antenatal care	X	
Postnatal care	X	
Knowledge and consumption of study specific intervention products	X	X
Knowledge and practices on Water, sanitation and hygiene (WASH)	X	X
Initiation of breastfeeding	X	X
Infant and young child feeding indicators (IYCF)	X	X
Child illness	X	X
Adherence	X	X

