9.2.1 Primary analysis

The intended primary analysis (primary outcome) will be conducted by [name] using SPSS once a clean dataset is available.

Study 1 and 2:

Anthropometric indices derived from measurements collected during study 1 and study 2 will be calculated using the WHO Child Growth Standard. Differences will be considered significant if $p < 0.05$, and interactions will be considered significant if $p < 0.1$. Covariates will include at least household socio-economic status, sex, and age. Regression models will be applied to analyse the effect of programme adherence.

Mean change in LAZ or HAZ measures will be compared between the two study arms in both studies using linear regression analysis. Details of the statistical methods will be outlined in the statistical analysis plan that will be elaborated once the protocol has been reviewed by the advisory board and approved by the ethics committees.

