9.2.3 Interim analyses

An interim analysis comparing birth length and weight between the intervention and control group as well as indicators collected during pregnancy (MUAC, weight, haemoglobin) will be conducted.

Further, small basic interim analysis after each round of data collection will be conducted in order to use them for interim reports which will only contain the most highly-relevant information and will be sent to the advisory board members.

These interim analyses will be performed by another statistician in order to make sure that [name] remains blinded for the main analysis.

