10. PLAN FOR COMMUNICATING FINDINGS OF THE STUDY

10.1 Dissemination strategy

The dissemination of the evaluation will be conducted using four concurrent dissemination activities.

1. Reporting of study results: The results from the various studies will be documented in multiple study reports, produced following each round of data collection for the two studies. Reports containing data from one data collection round will contain only the most highly-relevant information to make programmatic decisions. Following the completion of all data collection rounds for each evaluation activity, a comprehensive report will be produced containing all relevant information.
2. Peer-reviewed publications: Following completion of the various reports, further analyses on the data will be conducted and manuscript(s) will be submitted to peer-reviewed journals.
3. Presentation at national and international meetings and conferences: Following the completion of the study reports, results, in part or as a whole, will be presented to stakeholders. In addition, abstracts describing key results will be submitted for presentation at relevant meetings and conferences.
4. At the end of the study, the participating communities will be informed about the results of the study. This will include findings on the main study outcomes but also findings on product adherence and acceptability of the participating women and children. Possible next steps depending on the findings will also be highlighted to the communities.

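### As written, the analyst blind cannot last until all analysis is complete, because that analysis includes adherence models whose data identify the intervention arm

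*Protocol*

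**What the plan says.** Protocol section 9.2 sets an intention-to-treat comparison and gives as part of the reason that "adherence is one of the outcomes". It then describes a researcher-blinded analysis in which "the data analyst will not be provided with the keys to the group assignments before completion of data analysis".

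Section 9.2.1 (primary analysis) states: "Regression models will be applied to analyse the effect of programme adherence". Section 9.2.2 repeats the sentence for the secondary analyses.

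The data for those models are collected in both studies:

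- In Study 1, section 7.1 says that after round 1 "participants randomly allocated to the intervention group will start receiving the intervention package", and that at monthly household visits "the CHV will also collect data on intervention adherence and recent morbidity". Table 3 also marks adherence at rounds 2 to 5.
- In Study 2, Table 4 marks adherence to and coverage of the package at rounds 2 and 3.
- Table 10 (section 8.2.1) lists a module on "Knowledge and consumption of study specific intervention products" for both studies.

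On interim work, section 9.2.3 plans "An interim analysis comparing birth length and weight between the intervention and control group", together with indicators from pregnancy, and small analyses after each round for reports to the advisory board. All of these go to a different statistician, so that the main analyst stays blinded for the main analysis. Section 10.1 describes study reports "produced following each round of data collection for the two studies".

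**The concern.** Withholding a key blinds an analyst only if nothing else in the file reveals the groups. Here the analyst has to complete models of adherence to products that the study gives to one arm, and has to do so before receiving the key. The information that the key protects is then already in the analyst's hands.

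This matters because the protocol describes no other masking: participants and field staff know who receives the package. Analyst blinding is the one safeguard it offers, and some choices remain for it to protect. Sections 9.2.1 and 9.2.2 give the covariates as a minimum list of three (socio-economic status, sex, age). Section 9.2.2 leaves open whether non-normal secondary outcomes are transformed or analysed by non-parametric methods. If such choices are settled after the adherence data have been seen, the results would be reported as blinded when they were not.

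**Working it through.** The protocol gives no figure to reproduce, and the point depends on no significance level, power, standard deviation or dropout rate. The check sets the passages side by side.

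1. **When is the key released?** At completion of data analysis (9.2). No passage provides an earlier or staged release.

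2. **What must be complete by then?** At least the analyses in 9.2.1 and 9.2.2, and both include the adherence regressions. Section 9.2 also counts adherence among the outcomes. Read literally, the adherence models precede the key.

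3. **What data do those models need?** Product adherence and consumption records. It is an inference that the analyst holds them, because no sentence says so. It is a necessary inference for whoever runs the models, since adherence cannot be modelled without adherence data. No passage withholds these variables from the main analyst.

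4. **Do those data reveal the arm?** By section 7.4, the lipid-based supplements (Study 1) and the micronutrient powder (Study 2) go to the intervention arm only. They are not among the goods that section 7.1 offers to control households. Control records will be blank or near zero, so one table of supplement or powder use by coded group shows which code is the intervention. As an illustration, the retention factors in 7.2 give 600 × 0.95 × 0.80 × 0.95 × 0.75 = 324.9, about 325 Study 1 children per arm at 24 months. If 60–90% of intervention and 0–5% of control households reported use (an assumed range, not in the protocol), the two groups could not be confused. The conclusion does not depend on that range.

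5. **Do the statements of scope agree?** Section 9.2 runs the blind to the end of data analysis. Section 9.2.3 describes it as protecting the main analysis. The second can be achieved; the first, combined with step 2, cannot.

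6. **What about the interim results?** One interim comparison is explicitly by arm: birth length and weight, with the pregnancy indicators. Birth length gives the starting value of the Study 1 primary outcome, which is change in length-for-age z-score from birth to 24 months (7.2, 8.2). A separate statistician performs this work. The protocol does not say that by-arm content, in this interim or in the section 10.1 reports, is kept from the main analyst.

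**The case against.** The best defence is that the comparison that matters most can be blinded. Section 9.2.1 specifies linear regression of mean change in length- or height-for-age z-score, and that can be run on coded arms without any product variable. Nothing says that the primary dataset contains such variables. Names are removed from the public text, so it cannot be confirmed that one person runs every analysis or has the live data access described in section 8.4. Staged file release is often left to an analysis plan, and 9.2 promises one well before the analysis.

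Much of this stands, and it limits the point to the blind as written. It does not remove the point. Section 9.2 itself fixes when the key is released, so an analysis plan that released it after the primary comparison would depart from the protocol's wording.

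A reader might infer more than the documents support:

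- **That results by arm are circulated after every round.** Only one interim is stated to be by arm. The per-round reports go to the advisory board, all interim work goes to another statistician for the express purpose of protecting the blind, and section 10.1 does not say that its reports show results by arm.
- **That the analyst can shape data edits knowing the arm.** Section 9.1 ties edits to checks of incoming data and query forms, and 9.2.1 starts the analysis from a clean dataset.
- **That any product variable gives the arm away.** Soap, eggs, water treatment and rehydration salts can be found in control households too; Table 1 treats soap and water as a general household indicator. The argument rests on the supplement and powder data.
- **That no blind is possible in this trial.** The primary comparison shows otherwise.

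**Conclusion.** The point holds in a limited form. As worded, section 9.2 promises a blind up to the completion of data analysis, while 9.2.1 and 9.2.2 place inside that analysis models whose data identify the intervention arm. The promise and the tasks are incompatible, and 9.2.3 states a narrower scope.

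The consequence is moderate. No estimate, error rate or sample size changes by calculation, and the documents give no basis for putting a number on any bias. What is affected is the accuracy of a claim of blinded analysis and its protection of the covariate set and the secondary-outcome methods, so far as the analysis plan leaves these open. The conclusion assumes that the blinded analyst also runs the adherence models or otherwise receives their data, which the protocol implies but does not state. The change is worth making before the analysis starts, and it requires no change to design, sample or conduct.

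**What to change.** Reconcile 9.2 with 9.2.1, 9.2.2 and 9.2.3 as follows:

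1. Restate 9.2 so that the analyst is blinded until the primary and main secondary between-arm comparisons are locked.
2. Up to that lock, give the main analyst a file with coded arm, cluster, baseline covariates and outcome measurements only, leaving out adherence, product-use and training variables.
3. After the lock, release the key and the remaining variables for the adherence, programme and unintended-effect analyses, and describe these as unblinded.
4. State in 9.2.3 and 10.1 that the by-arm interim results on birth size and pregnancy indicators, and any by-arm content in round reports, are not shared with the main analyst before the lock.

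The cost is protocol wording, one extra data export and slightly later adherence analyses. Reports to the advisory board can continue as planned.

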9.2.1 Primary analysis

The intended primary analysis (primary outcome) will be conducted by [name] using SPSS once a clean dataset is available.

Study 1 and 2:

Anthropometric indices derived from measurements collected during study 1 and study 2 will be calculated using the WHO Child Growth Standard. Differences will be considered significant if $p < 0.05$, and interactions will be considered significant if $p < 0.1$. Covariates will include at least household socio-economic status, sex, and age. Regression models will be applied to analyse the effect of programme adherence.

Mean change in LAZ or HAZ measures will be compared between the two study arms in both studies using linear regression analysis. Details of the statistical methods will be outlined in the statistical analysis plan that will be elaborated once the protocol has been reviewed by the advisory board and approved by the ethics committees.

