- maternal BMI (body mass index)
- maternal age
- maternal education
- gestational age at enrolment
- parity
- time interval from prior birth
- household socio-economic status
- household food insecurity
- site

The following additional parameters assessed at round 3 (delivery) have been defined as independent variables for study endpoint outcomes:

- child sex
- mode of delivery

The following parameters assessed at baseline have been defined as independent variables to potentially influence the outcome at round 2 and 3 of **study 2**:

- maternal age
- maternal education
- parity
- time interval from prior birth
- child sex
- household socio-economic status
- household food insecurity
- whether cluster received health insurance (other study taking place in the same district)
- site

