7.2 Sample size and randomization

Study 1 and 2:

Some indicators included in study 1, such as maternal haemoglobin, child haemoglobin, and child length-for-age z score (LAZ), are measured more than once in the same study subject over time. This is also the case for haemoglobin and height-for-age z score (HAZ) in the children in study 2. For these indicators, the average change in outcomes in study subjects in the intervention group will be compared to the average change in study subjects in the control group. Other indicators in study 1, such as birth weight and length, are measured only once in each study subject. For these indicators, the average value in the intervention group will be compared to the average value in the control group.

The sample size depends on the size of the desired minimum difference between the intervention group and the control group, which can be detectable with statistical significance. This minimum

difference is expressed as the effect size, which is the difference in the value of the indicator between the two groups to be compared divided by the standard deviation of the indicator. For those outcomes measured more than once, the indicator is the change over time in study subjects. This effect size can be written as follows:

$$\frac{[\text{Mean}(LAZ_{C_x} - LAZ_{C_y})_{\text{Group1}} - \text{Mean}(LAZ_{C_x} - LAZ_{C_y})_{\text{Group2}}]}{\text{Standard deviation}(LAZ_{C_x} - LAZ_{C_y})_{\text{Group1}}}$$

Where C_x and C_y stand for the two measurements of those indicators which are measured twice.

The sample size calculations make the following assumptions: 1) a two-tailed comparison (that is, there is no *a priori* conclusion about which group is higher and which is lower), 2) statistical significance is defined as a p value less than 0.05, 3) the power of the study is at least 0.8, and 4) that the standard deviation of the indicator in both study groups is the same.

Although it is difficult to find highly comparable interventions and their effect sizes for key outcomes put forth, Table 5 below provides an overview of observed effect sizes for somewhat similar interventions and outcomes.

Table 5: Effect sizes in children for similar outcomes and interventions reported in the literature

Description of intervention	Reported outcome	Effect size (95%CI)	Reference
Maternal education on complementary feeding and provision of complementary foods	Weight gain	0.34 (0.11, 0.56)	[35]
	Linear growth	0.26 (0.08, 0.43)	

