children would still be enrolled at final data collection at 24 months of age. Taking into account all these assumptions for the recruitment of a total of 1,200 pregnant women (600 women in the control and 600 women in the intervention group) in 120 clusters this will allow detecting an effect size of 0.26 in LAZ in children between 6-24 months of age, which is a reasonable effect size when compared to another study in which LNS was used during pregnancy and infancy (Table 5). Effect sizes for changes in haemoglobin concentration in children, one of the secondary outcomes in our study, are higher than for linear growth and thus our sample size will allow detecting changes in this indicator (Table 5).

Sample size was also calculated for birth weight. From prior studies of birth weight in less-developed countries, an average birth weight in the study population of 3,000 g, a standard deviation of 500 g, and a birth weight 85 g larger in the intervention population was assumed. Furthermore, it was assumed that the study drop out will be at 20%. A sample size of about 1,090 women is needed, or 545 per study arm which is covered with the calculation for the primary outcome with 600 women per arm.

For study 2, considering logistical challenges we estimated that a maximum of 2,000 children 6-35 months of age could be recruited. The primary outcome is change in length-for-age z-score (LAZ) between enrolment and after 2 years of follow up. The effect size that is detectable takes into account the design effect of cluster randomization (design effect = 1.3) as in study 1 and assumes that caregivers of 95% of eligible children would consent to participation and that 80% of enrolled children would complete the 2 years follow-up. Taking into account all these assumptions for the recruitment of a total of 2,000 children (1,000 children in the control and 1,000 children in the intervention group) in 100 clusters this will allow detecting an effect size of 0.17 in LAZ or HAZ in children between baseline and 2 years follow up, which is a reasonable effect size and has been shown in other studies before (Table 5). As in study 1, our sample size will allow detection of changes in haemoglobin concentration as effect sizes are higher than for linear growth (Table 5).

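### Study 2: naming round 1 LAZ/HAZ as a covariate in the primary model would be a free gain in precision, not the repair of an error

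*Protocol*

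**What the plan says.** Protocol 7.2 defines the Study 2 endpoint: "The primary outcome is change in length-for-age z-score (LAZ) between enrolment and after 2 years of follow up". The comparison is between arm means of change: "the average change in outcomes in study subjects in the intervention group will be compared to the average change" in the control arm. The effect size is on the same scale: "For those outcomes measured more than once, the indicator is the change over time in study subjects", divided by the SD of that change.

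Protocol 9.2.1 names linear regression for this comparison and sets the adjustment: "Covariates will include at least household socio-economic status, sex, and age". It leaves further detail to a statistical analysis plan, which was not available for this review.

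Section 5 has a separate Study 2 list, introduced by "The following parameters assessed at baseline have been defined as independent variables to potentially influence the outcome at round 2 and 3 of" that study. It holds maternal age, maternal education, parity, birth interval, child sex, socio-economic status, food insecurity, the health insurance intervention and site. Round 1 LAZ/HAZ is in neither place.

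Section 7.1 and Table 4 put height and weight in round 1, before any product is distributed. Section 9.2.4 keeps children who lack one of the two paired measurements out of the change analysis, so every child in that analysis has a baseline value.

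**The concern.** The baseline value of a continuous outcome is usually its strongest predictor. A change score without a baseline term subtracts the whole baseline value, which is the same as fixing the slope of the 2-year value on baseline at 1. When the true slope differs from 1, the arm comparison carries avoidable noise.

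Precision cannot easily be bought in another way here. Section 7.2 gives 2,000 children as the most that logistics allow. Some of the linear growth effects that Table 5 cites fall below the detectable 0.17: 0.04 (-0.13, 0.22) for micronutrient powders, and 0.0 to 0.14 for programmes of complementary foods with feeding education. Others, at 0.21 to 0.26, lie above it. Section 11.1 also warns that the wide age range makes the sample more heterogeneous. The choice of a baseline covariate is best fixed before outcome data are seen.

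**Working it through.** **Inputs from Protocol 7.2.** 1,000 children per arm in 100 clusters; 95% consent; 80% completion; design effect 1.3; "a two-tailed comparison"; "statistical significance is defined as a p value less than 0.05"; "the power of the study is at least 0.8". Stated detectable effect: 0.17 SD of change.

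**Reproducing the stated figure.**
- Completers per arm: 1,000 × 0.95 × 0.80 = 760.
- Effective number per arm: 760 / 1.3 = 584.6.
- Standard error in SD-of-change units: √(2/584.6) = 0.0585.
- Detectable effect, normal formula: 2.8016 × 0.0585 = 0.1639. With t on 98 degrees of freedom it is 0.1655, which rounds to 0.17. The stated figure stands.
- Power at 0.17, normal formula: 82.8%.

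**Effect of adding baseline.** The protocol gives neither the correlation r between baseline and 2-year LAZ nor the LAZ SDs. Both are assumptions here, and covariates other than baseline are ignored. With a common SD s at both rounds:
- Variance of change: 2s²(1 − r).
- Residual variance given baseline: s²(1 − r²).
- Ratio: (1 + r)/2. Share of variance saved: (1 − r)/2.

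The detectable effect scales with √((1 + r)/2), keeping the design effect at 1.3. It stays in SD-of-change units. The last column is 2,000 × (1 + r)/2.

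| r | Variance saved | Detectable effect | Power at 0.17 | Recruits giving the precision of unadjusted change in 2,000 |
|---|---|---|---|---|
| no baseline term | – | 0.1639 | 82.8% | 2,000 |
| 0.3 | 35% | 0.1321 | 95.0% | 1,300 |
| 0.5 | 25% | 0.1419 | 91.9% | 1,500 |
| 0.6 | 20% | 0.1466 | 90.1% | 1,600 |
| 0.7 | 15% | 0.1511 | 88.4% | 1,700 |
| 0.8 | 10% | 0.1555 | 86.5% | 1,800 |
| 0.9 | 5% | 0.1597 | 84.7% | 1,900 |

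**Check under clustering.** A simulation used 100 clusters of 15 children, an intracluster correlation of 0.021 (from 0.3/14.2), equal SDs, and the same r at cluster and child level. The variance saved was 25%, 16% and 10% at r = 0.5, 0.7 and 0.8, in line with the formula.

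**Unequal SDs.** With q = SD at 2 years / SD at baseline, the ratio is q²(1 − r²)/(1 + q² − 2rq). At r = 0.8:
- q = 0.9: 0.2916/0.37 = 0.788, so 21% is saved.
- q = 1.1: 0.4356/0.45 = 0.968, so 3% is saved.
- q = 1.25: 0.5625/0.5625 = 1, so nothing is saved. This is the general case r × q = 1, where the true slope is already 1.

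**Why the outcome need not change.** If change = a + τ·arm + b·baseline, then 2-year value = a + τ·arm + (b + 1)·baseline. The arm coefficient τ is the same.

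**The case against.** The strongest objection is that this belongs to the statistical analysis plan. The words *at least* in 9.2.1 make an open minimum, details are expressly deferred, and nothing in the protocol excludes baseline LAZ. The section 5 list is no closed specification either: it omits child age, which 9.2.1 requires. All of this stands. A reader might infer that the plan has decided against baseline adjustment, and the documents do not support that. What remains is that the protocol has already chosen the change score and a minimum covariate set, and leaves the most useful covariate optional.

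A second objection is that nothing is broken. That is also right. A reader might infer a biased or underpowered primary test. But the change score is unbiased under randomisation, the sample size is built on the SD of change, and power at 0.17 is 82.8% without adjustment. Chance baseline imbalance between arms is already inside the standard error; it is the same loss of precision seen from another side, not a further one.

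Third, the size of the gain is conditional. It would be wrong to say that a change score is less precise whenever r is below 1: when r × (SD at 2 years / SD at baseline) equals 1, the two methods are equally precise. The 10% to 25% is not a property of this trial, because the protocol gives no correlation and no SDs. The planned model also adjusts for socio-economic status, sex and age, so the comparison with a change score that has no covariates only approximates the gain over the actual plan.

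**Conclusion.** This is a free improvement and not an error. The protocol does not name round 1 LAZ/HAZ as a covariate for the Study 2 primary outcome, although the value will be in hand for every child analysed. Adding it would usually narrow the interval.

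Under equal SDs and r from 0.5 to 0.8, and leaving the other covariates aside, the gain is that of the r = 0.5 to 0.8 rows of the table above. Widening r to 0.3 to 0.9 gives 35% to 5% of the variance. Unequal SDs move the figure in either direction, down to zero in the special case shown. The stated detectable effect of 0.17 is not in question. The calculation covers the Study 2 primary outcome only.

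**What to change.** In 9.2.1, add a sentence for Study 2: the regression of change in LAZ/HAZ on arm includes round 1 LAZ/HAZ as a covariate, alongside child age, sex and socio-economic status. Add round 1 LAZ/HAZ to the Study 2 list in section 5, and carry the same wording into the statistical analysis plan.

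Confine the sentence to Study 2. Section 9.2.1 covers both studies, and in Study 1 LAZ at birth is measured after the intervention has begun in pregnancy, so it is not a pre-intervention baseline.

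The named outcome and the sample size can stay as they are. No new data are needed, and no child leaves the analysis, because 9.2.4 already requires both measurements.
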